## Study Information

Title	Treatment Patterns and Clinical Outcomes Among Indian Patients Receiving Palbociclib Combinations for HR+/HER2- Advanced/Metastatic Breast Cancer in Real World Settings
Protocol number	A5481145
Protocol version identifier	Version 1.0
Date	19/10/2020
Active substance	L01XE33  Palbociclib
Medicinal product	Palbace (palbociclib)
Development phase	This is a retrospective, non-interventional study (NIS)
Population of interest	Adult female patients with HR+/HER2- advanced/metastatic breast cancer
Research question and objectives	To describe patient demographics, clinical characteristics, treatment patterns and clinical outcomes of adult female patients who have received palbociclib combination treatments for hormone receptor positive/ human epidermal growth factor 2 negative (HR+/HER2-) advanced/metastatic breast cancer in real world settings in India.  Primary objectives 

• To describe demographics and clinical characteristics of patients who have received

PFIZER CONFIDENTIAL

	
palbociclib combination with aromatase inhibitor (as prescribed by the Physician) in menopausal state as initial endocrine therapy in MBC or with fulvestrant after progression on prior endocrine therapy.
 

• To summarize adjuvant therapies received for the treatment of early or locally advanced breast cancer (Stages 0-IIIa).

• To describe treatments received in the advanced/metastatic setting, before and after palbociclib combination use.

• To describe dosing and dose changes, interruptions, delays, and discontinuations associated with palbociclib use in clinical practice.

• To describe supportive therapies received by patients while receiving palbociclib combination treatments.

• To determine in overall population and defined subgroups, clinical outcomes including (but not limited to):

• Proportion of patients who are progression free at specific intervals (eg, 6, 12, 18 months).

• Objective response rate (ORR) – depending on availability of follow-up data.

• Proportion of patients alive after 1 and 2 years post palbociclib combination initiation - depending on availability of follow-up data (sample size permitting).

--	---

Country	India

## 2. LIST OF ABBREVIATIONS

Abbreviation	Definition
ABC/MBC	advanced/metastatic breast cancer
AE	adverse events
AEM	adverse events monitoring
CDK	cyclin-dependent kinase
CDSCO	Central Drugs Standard Control Organization
DFI	disease free interval
eCRF	electronic case report form
ECOG	Eastern Cooperative Oncology Group
EDC	electronic data capture
ER	estrogen receptor
GPP	Guidelines for Good Pharmacoepidemiology practices
HER2	human epidermal growth factor receptor 2
HR	hormone receptor
HR+/HER2-	Hormone receptor positive / human epidermal growth factor 2 negative
IEC	independent ethics committee
IRB	institutional review board
ISPE	International Society for Pharmacoepidemiology
LHRH	Leutinizing Hormone Releasing Hormone
NI	non-interventional
NIS	non-interventional study
ORR	objective response rate

OS	overall survival
PALOMA	Palbociclib: Ongoing Trials in the Management of Breast Cancer
PFS	progression free survival
PHI	protected health information
SAP	statistical analysis plan
SAS	Statistical software suite developed by SAS Institute for advanced analytics
CCI	
USFDA	United States Food and Drug Administration
YRR	your reporting responsibility

### 4. ABSTRACT

**Title:** Treatment Patterns and Clinical Outcomes Among Indian Patients Receiving Palbociclib Combinations for HR+/HER2- Advanced/Metastatic Breast Cancer in Real World Settings.

**Rationale and background:** Breast cancer is a leading cause of cancer-related death in females worldwide. An approximately 75% of all breast cancer are diagnosed to be HR positive (HR+) which grow in response to increased levels of the hormones estrogen and progesterone. Palbociclib is a first in class CDK4/6 inhibitor that has been approved for use in HR+/HER2- advanced/metastatic breast cancer (ABC/MBC) patients. The approval of palbociclib combination treatment was based on the results of the 3 globally conducted PALOMA (Palbociclib: Ongoing Trials in the Management of Breast Cancer) trials. In India palbociclib, in combination with letrozole, was approved in the month of August 2016. It has been more than 2 years since palbociclib has been used in India for the treatment of HR+/HER2- advanced/metastatic breast cancer (ABC/MBC) patients. However there is

scarce information regarding how and when palbociclib combination is prescribed in routine clinical practice, and the outcomes associated with palbociclib use. Therefore, real world data on the characteristics, treatment patterns and clinical outcomes among patients receiving palbociclib combinations to treat HR+/HER- ABC/MBC will provide valuable insight to help inform treatment decisions.

**Research question and objectives:** The primary objective of this real world study is to describe the patient demographics, clinical characteristics, treatment patterns, and clinical outcomes of adult female patients who have received palbociclib combination treatments for HR+/HER2- ABC/MBC in real world settings in India.

**Study design:** This retrospective physician based medical record review will collect data from medical records of patients, who have received palbociclib combination with aromatase inhibitor (as prescribed by the Physician) in menopausal state as initial endocrine therapy in MBC or with fulvestrant after progression on prior endocrine therapy. Data will be collected retrospectively at a single point in time from patient medical records.

**Population:** Data will be collected from the Indian routine clinical practice settings. Approximately 10 oncologists will be included. To be eligible to participate, physicians must have treated, or be treating 10 or more HR+/HER2- ABC/MBC patients with palbociclib combination with aromatase inhibitor (as prescribed by the Physician) in menopausal state as initial endocrine therapy in MBC or with fulvestrant after progression on prior endocrine therapy. Each physician will complete at least 10-15 electronic case report forms (eCRFs). Included physicians must go back in their records to the specific index date and select the next number of eligible patients for which they will complete eCRFs. The 'index date' will be defined as 60 days after the physician first prescribed palbociclib + partner therapy following the availability of specific indication in the market. To be eligible, patients must be females, aged 18 or over, have been diagnosed with HR+/HER2- ABC/MBC and must have received palbociclib combination with aromatase inhibitor (as prescribed by the Physician) as initial endocrine therapy in postmenopausal MBC patients or with fulvestrant in patients who have progressed on prior endocrine therapy. For the study, patients must have initiated palbociclib with fulvestrant a minimum of 3 months, or palbociclib with aromatase inhibitor a minimum of 6 months prior to data collection.

**Variables:** The variables assessed in this study will be patient demographics at the time of data collection, clinical characteristics, comorbid conditions, early and advanced breast cancer treatment history, palbociclib treatment patterns including dose changes, clinical outcomes and date of death if applicable.

**Data sources:** Patient medical records will be used as the data source for the study.

**Study size:** Approximately 10 physicians will be recruited across the India; this will enable data to be collected for approximately 150 patients.

**Data analysis:** All analyses will be descriptive in nature. Categorical variables will be described using the number of observations and number and percent (%) in each category.

Numeric variables will be described using the number of observations, mean and standard deviation, and minimum, maximum, median and interquartile range. Time to event will be described using a Kaplan-Meier chart for the median.

**Milestones:** Data collection will begin in November 2020 and should be completed by January 2021. Following completion of the study, the final report will be written and completed by February 2021.

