## 9. RESEARCH METHODS

### 9.1 Study Design

This is a post marketing, retrospective, non-interventional study (NIS). The study will be conducted as a retrospective medical record review of patients who have received palbociclib combination with aromatase inhibitor (as prescribed by the Physician) in menopausal state as initial endocrine therapy in MBC or with fulvestrant after progression on prior endocrine therapy. It will comprise of an initial screening and eligibility assessment of patients followed by data collection from eligible patient records.

Data collection will be conducted using a predesigned electronic case report form (eCRF). Eligible physicians will be invited to complete the eCRF of patients that meet the study criteria. Each eCRF will take around 25 minutes to complete. Patient eligibility will be confirmed by treating physicians. In order to allow for a sufficiently long observational window, treating physicians will be asked to go back to a specific point in time, the index date, and sequentially select the medical records of the next 'n' patients who meet the inclusion criteria. The 'index date' will be defined as 60 days after the physician first prescribed palbociclib + partner therapy following the availability of specific indication in the market (eg, if palbociclib + aromatase inhibitor was available on 25 October 2016 in India and the physician initiated a patient on palbociclib with aromatase inhibitor the next day, the index date will be 26 December 2016). The index date will differ for the specific indications/combination partners if approved on different dates.

The proportion of patients treated in accordance with the first line versus second or later line setting for metastatic disease will be approximately 7:3, as has been observed in the real world practice.

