## 9.2 Setting

Data will be collected from approximately 10 physicians recruited across India. Each physician will complete at least 10-15 eCRFs. Data will be collected retrospectively at a single point in time from patient medical records.

Initial screening questions/recruitment criteria will ensure the relevant physicians are selected and all other non-qualifying physicians will be excluded. In addition, during physician recruitment a representative geographical split and private/public practice split will be sought where possible to ensure a representative sample.

To be eligible, physicians must have treated or be treating 10 or more HR+/HER2- ABC/MBC patients who meet the eligibility criteria for the study. This will ensure that recruited physicians will be able to complete the minimum number of eCRFs required to participate in the study. Once physicians have been recruited, they must go back to a specific index date, defined in [Section 9.1](#) and select the next number of eligible patient records from patients who have been treated with a palbociclib combination. The consecutive approach to recruitment will be stressed to each participating physician to limit selection bias.

Each participating physician and patient must meet the following criteria to be eligible for the medical record reviews.

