### 9.3 Variables

**Table 1. List of Study Variables**

Variable	Role	Data Source(s)	Operational Definition
Patient demographics	Baseline Sub-group identifier	Patient records	Age, ethnicity, weight, height, biomarker status, family history of breast cancer.
Clinical characteristics	Baseline Sub-group identifier	Patient records	Time since diagnosis, staging, node status, menopause status. ECOG/Karnofsky functional status, diagnosis for which palbociclib combination was prescribed, sites of metastases, de novo vs. recurrent disease.
Comorbid conditions	Baseline Sub-group identifier	Patient records	Comorbid conditions.
Early treatment history	Baseline Sub-group identifier	Patient records	Adjuvant treatments received since breast cancer diagnosis, time since end of adjuvant treatment, surgery/radiotherapy received.
Advanced treatment history	Baseline Sub-group identifier	Patient records	Treatments and supportive therapies received since metastatic/advanced HR+/HER2- diagnosis, duration of treatments, reasons for regimen changes.
Palbociclib combination treatment	Exposure Sub-group identifier	Patient records	Starting dose, duration of treatment, line of treatment, changes in dose, interruptions, cycle delays and discontinuations; where possible reasons for change in treatment.
Clinical outcomes	Outcomes	Patient records	Proportion progression free, ORR, TTP, PFS, patient death, 1-year and 2-year survival in all patients and within specific subgroups.

PFIZER CONFIDENTIAL

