7.2 STATISTICAL ANALYSES

- **Demographic Characteristics**

The demographic and baseline characteristics will be summarized by using descriptive statistics. Continuous variables such as age will be summarized by number of observations (n), arithmetic mean (mean), standard deviation (SD), median, minimum value (min), and maximum value (max) and Categorical variables such as menopausal status, induced menopause, family history of breast cancer and patient deceased will be presented by frequency (n) and percentage (%).

- **Initial and advance breast cancer diagnosis**

For all the patients initial diagnosis of breast cancer stages (stage 0 to stage IV) will be presented in frequency counts (n) and percentage (%). For the advance stages (stage IIIb, IIIc or IV) of breast cancer patients again locoregionally advanced or metastatic frequency counts (n) and percentage (%) will be given. For the metastatic disease, sites of metastases such as Bone, Liver, Brain, Lung, Lymph nodes and others with further segregation like single or multiple locations will be presented in frequency (n) and percentage (%).

- **Prior Therapy**

For all patient's prior therapy type (Targeted, Endocrine and Chemotherapy) will be presented by frequency count and percentage

- **Performance status**

Performance status using ECOG scale at the initiation of palbociclib treatment. Status is measured using 4 point scale from fully active to completely disable and will be summarized by frequency (n) and percentage (%).

- **Early Breast Cancer Treatment History**

Following early breast cancer diagnosis treatments received such as surgery, radiotherapy, neoadjuvant treatment, adjuvant chemotherapy, adjuvant endocrine therapy by patients will be summarized by frequency (n) and percentage (%).

- **Palbociclib Treatment**

PFIZER CONFIDENTIAL

For all the patients initial dose prescribed of palbociclib, any dose adjustments made to palbociclib and for each dose adjustment if dose reduced or increased, palbociclib was temporarily interrupted, cycle delay and reason for dose change will be summarized by frequency (n) and percentage (%). Moreover, complete summary (frequency and percentage) of all supportive therapies that patients received will be presented.

- **Advance Breast Cancer Treatment History**

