10 APPENDICES

10.1 APPENDIX 1: MOCK SHELLS FOR TABLES

Table 1 Demographic Characteristics – All Subjects

Characteristic (Unit)	Statistics	Palbociclib (N=xx)
Age of the patients	n	xx
	Mean (SD)	xx.x (xx.xx)
	Median	xx.x
	Min, Max	xx, xx
Age group >65 yrs vs <65 yrs	n (%)	
Menopause Status		
Induced	n (%)	xx (xx.x)
Natural	n (%)	xx (xx.x)
Type of Induced Menopause		
LHRH suppression	n (%)	xx (xx.x)
Radioablation	n (%)	xx (xx.x)
Surgical	n (%)	xx (xx.x)
Patient deceased		
No	n (%)	xx (xx.x)
Yes	n (%)	xx (xx.x)
Family History of Breast Cancer		
No	n (%)	xx (xx.x)
Yes	n (%)	xx (xx.x)
Abbreviations: N = number of subjects in Palbociclib group; n = number of subjects in specified category; LHRH = Luteinizing Hormone Releasing Hormone		
Note 1: Percentages are based on the number of subjects in the Palbociclib group.		
Table 1.1 Demographic Characteristics by line of treatment (first line vs. second and later line)		

PFIZER CONFIDENTIAL

Table 2 Initial and Advance Breast Cancer Diagnosis– All Subjects

Characteristic (Unit)	Statistics	Palbociclib (N=xx)
Stage of Breast Cancer at diagnosis		
Stage I	n (%)	xx (xx.x)
Stage II	n (%)	xx (xx.x)
Stage IIIa	n (%)	xx (xx.x)
Stage IIIb	n (%)	xx (xx.x)
Stage IIIc	n (%)	xx (xx.x)
Stage IV	n (%)	xx (xx.x)
Type of breast cancer (Metastatic/ locally advanced)		
Locoregionally advanced	n (%)	xx (xx.x)
Metastatic	n (%)	xx (xx.x)
Abbreviations: N = number of subjects in Palbociclib group; n = number of subjects in specified category		
Note 1: Percentages are based on the number of subjects in the Palbociclib group.		
Table 2.1 Initial and Advance Breast Cancer Diagnosis by line of treatment (first line vs. second and later line)		

Table 3 Advance Breast Cancer Diagnosis – All Subjects

PFIZER CONFIDENTIAL

Characteristic (Unit)	Statistics	Palbociclib (N=xx)
Sites of Metastases		
Bone	n (%)	xx (xx.x)
Lung	n (%)	xx (xx.x)
Liver	n (%)	xx (xx.x)
Lymph nodes	n (%)	xx (xx.x)
-----	-----	-----
-----	-----	-----
Bone		
Single site	n (%)	xx (xx.x)
Multiple sites	n (%)	xx (xx.x)
Liver		
Single site	n (%)	xx (xx.x)
Multiple sites	n (%)	xx (xx.x)
Lung		
Single lung	n (%)	xx (xx.x)
Bilateral	n (%)	xx (xx.x)
Pleural effusion	n (%)	xx (xx.x)
Lymph Nodes		
Regional	n (%)	xx (xx.x)
Distal	n (%)	xx (xx.x)

Abbreviations: N = number of subjects in Palbociclib group; n = number of subjects in specified category

Note 1: Percentages are based on the number of subjects in the Palbociclib group.

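### The only time point given for demographics is data collection, although they serve as baseline variables; age should be anchored to palbociclib initiation

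*Protocol*

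**What the plan says.** The Variables paragraph of the protocol abstract (section 4) puts the demographics at a stated moment: "patient demographics at the time of data collection".

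Protocol section 9.3, Table 1, defines the demographic items as "Age, ethnicity, weight, height, biomarker status, family history of breast cancer" and gives them the role "Baseline Sub-group identifier". It states no time point.

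SAP 7.2 says "The demographic and baseline characteristics will be summarized by using descriptive statistics". The SAP Table 1 shell (Appendix 1) has the row "Age of the patients" and a split above and below 65 years, neither with a reference date. The same shell reports whether the patient has died. By contrast, SAP 7.2 and the Table 5 shell tie ECOG performance status to palbociclib initiation.

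On timing, protocol 9.2 says "Data will be collected retrospectively at a single point in time from patient medical records", and the abstract says "Data collection will begin in November 2020 and should be completed by January 2021". Physicians select consecutive patients from an index date defined as "60 days after the physician first prescribed palbociclib + partner therapy" (protocol 9.1).

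**The concern.** Describing the demographics of the treated patients is part of the first primary objective. For that purpose age should be age at treatment start. A patient's age on the day the chart is abstracted is a different quantity. The gap between the two depends on when she started and on which partner drug she received, because the two combinations were approved at different times and have different minimum follow-up.

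The planned outputs at risk are the age summary, the 65-year split, and the version of that table by line of treatment (SAP Table 1.1). Eligibility links partner drug to treatment history, so the shift need not be equal in the two line-of-treatment columns.

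Death adds a second gap. The study includes patients who have died, and neither document says which age to enter for a patient who was no longer alive at data collection. Sites could resolve this differently, and protocol 9.8 plans no regular source data verification that would reveal it.

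**Working it through.** **1. The plan's own date example.** Protocol 9.1 takes a first prescription on 26 October 2016 and gives an index date of 26 December 2016. Adding 60 days gives 25 December 2016; the stated date is 61 days later. The one-day difference has no bearing here, and I use the stated date. The documents give no figure for the lag itself.

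**2. Minimum lag.** The inclusion criteria (protocol 9.2.1) require at least 3 months of follow-up since the start of palbociclib with fulvestrant, and at least 6 months with an aromatase inhibitor.

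**3. Maximum lag at the planned collection dates.** Lag = collection date − earliest selectable start, in days divided by 365.25. Collection is taken as 1 November 2020 to 31 January 2021. Approval months are from protocol section 7; a first prescription in the approval month is an assumption that gives the upper end.

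| Earliest start | To 1 Nov 2020 | To 31 Jan 2021 |
|---|---|---|
| Aromatase inhibitor, example index date 26 Dec 2016 | 1406 d = 3.85 y | 1497 d = 4.10 y |
| Aromatase inhibitor, 1 Aug 2016 + 60 d = 30 Sep 2016 | 1493 d = 4.09 y | 1584 d = 4.34 y |
| Fulvestrant, 1 Dec 2017 + 60 d = 30 Jan 2018 | 1006 d = 2.75 y | 1097 d = 3.00 y |
| Fulvestrant, 31 Dec 2017 + 60 d = 1 Mar 2018 | 976 d = 2.67 y | 1067 d = 2.92 y |

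The maximum is therefore about 3.9 to 4.3 years for an aromatase inhibitor and about 3 years for fulvestrant. The SAP cites a CRF version dated 20 May 2021. If collection ran to that date (an assumption), the aromatase inhibitor maximum would be 4.4 years from the example index date and up to 4.6 years from approval.

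**4. Illustrative effect on mean age.** Assumptions: starts are uniform over the eligible window, and the 7:3 line mix in protocol 9.1 is read as aromatase inhibitor to fulvestrant.

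- Aromatase inhibitor, 0.5 to 4.1 y: mean lag (0.5 + 4.1)/2 = 2.30 y
- Fulvestrant, 0.25 to 3.0 y: mean lag (0.25 + 3.0)/2 = 1.625 y
- Mixture: 0.7 × 2.30 + 0.3 × 1.625 = 2.10 y

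Mean age is overstated by the mean lag, about 2 years.

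**5. Illustrative effect on the 65-year split.** The share that moves is P(age at start < 65 and age at start + lag ≥ 65). I simulated this with normal ages and the lag mixture of step 4. The documents give no age distribution, so means of 55 to 60 and SDs of 10 to 11 are assumed. The shell does not place patients aged exactly 65; I count them in the older group.

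| Mean, SD | Share crossing 65 | Of 150 |
|---|---|---|
| 55, 11 | 5.6% | 8.3 |
| 58, 11 | 6.6% | 9.9 |
| 60, 10 | 7.8% | 11.7 |

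This is about 5.5 to 8%, or 8 to 12 of 150 patients. If all starts fell 0.5 to 1.5 years before collection, the share would be 2.5 to 3.6%.

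**The case against.** The best reply is that the phrase occurs once, in a one-sentence list in the abstract. The operative variable table gives a baseline role and no collection-date anchor, and the SAP does not repeat the phrase. The eCRF, which decides what is captured, is not among the documents. This stands in part. A reader might infer that age and weight are certain to be recorded late; the documents do not show that. They show one stated time point that conflicts with the stated role, and a SAP that does not settle the conflict. A programmer looking for a rule would still find only the abstract's.

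Three further readings go beyond the text:

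- **Weight has the same lag as age.** Weight and height are in protocol Table 1 but not in SAP 7.2 or the visible SAP Table 1 shell. In a chart review, the weight would be a charted value of unknown date.
- **Age cannot be defined for patients who died.** The documents only omit a rule. If birth date or year is captured, age at initiation can be derived for every patient. That sites would enter age at death is conjecture.
- **One lag of 0.5 to 4.3 years fits everyone.** That would give 6 to 9% crossing 65, and 10 to 14% if all lags were 3 to 4.3 years. It ignores fulvestrant's later approval and shorter maximum. Each physician's first prescription date is also unknown, so actual lags may be shorter.

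It is also fair to say that the consequence is limited. The study is descriptive, the SAP lists no subgroups beyond its breakdown by line of treatment, and no visible outcome analysis uses age (part of the outcome text is redacted).

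**Conclusion.** The point holds as a conflict between a stated time point and a stated role. The lag range follows from the documents' own dates and follow-up criteria; its upper end for each combination also assumes a first prescription in the approval month. The 2-year shift in mean age and the 5.5 to 8% crossing 65 are illustrations that rest on an assumed age distribution, an assumed even spread of starts and a reading of 7:3 as the partner mix. They show the order of magnitude and are not estimates for this cohort.

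The effect reaches the age summary and the 65-year split in SAP Tables 1 and 1.1. No error rate, sample size or visible outcome result depends on it. It should be corrected because it touches the first primary objective and the remedy is simple, but it does not threaten the study.

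**What to change.** 1. In the protocol abstract, replace the phrase with: *patient demographics at initiation of the palbociclib combination*.
2. Add the same anchor to the demographics row of protocol Table 1, to SAP 7.2 and to SAP Tables 1 and 1.1, including the 65-year split. This matches what the SAP already does for ECOG.
3. Derive age from the initiation date and the date or year of birth. If birth date is not captured, have the site record age at initiation. Either rule also covers patients who have died.
4. If weight and height are reported, use the charted value nearest to, and not after, initiation.

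The cost is one replaced phrase in the abstract and short additions elsewhere; SAP 7.2 has no timing phrase to replace. SAP Table 10 reports time from diagnosis to initiation, so a start date, or that interval, must be captured. Capture of birth date or year is not shown, and the data are de-identified. The eCRF therefore needs a check, and a small change if it holds only current age.
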